
**Table 4: Dosing Algorithm – Titration Period**

CCI

**Table 5: Dosing Algorithm – Maintenance Period**

## 6.6. CONTINUED ACCESS TO TRIAL INTERVENTION AFTER THE END OF THE TRIAL

Access to the trial drug after trial end will not be offered to any of the participants. Effective drugs for the indication are commercially available.

## 6.7. TREATMENT OF OVERDOSE

There is no antidote for somatropin overdose. Treatment is symptomatic and supportive. It is recommended to monitor thyroid function following an overdose.

In the event of an overdose, the investigator should:

- Contact the medical monitor immediately.
- Evaluate the participant to determine, in consultation with the medical monitor, whether trial intervention should be interrupted or whether the dose should be reduced.
- Closely monitor the participant for any AE/SAE and laboratory abnormalities until trial intervention can no longer be detected systemically or for at least 7 days.
- Obtain a plasma sample for PK analysis as soon as possible if requested by the medical monitor (determined on a case-by-case basis).
- Report as an AE in accordance with Section 8.3 and document the quantity of the excess dose as well as the duration of the overdose.

## 6.8. CONCOMITANT THERAPY

For participants receiving oral estrogen or estrogen-containing therapy, participants must intend to maintain the same dose and route of estrogen administration throughout the trial.

The following should be avoided during trial participation: weight-loss drugs or appetite suppressants, including orlistat, zonisamide, lorcaserin, bupropion, topiramate, sibutramine, stimulants (e.g., phentermine or ADHD medications such as amphetamines or methylphenidate), and GLP-1 receptor agonists (e.g., dulaglutide, exenatide, liraglutide, lixisenatide, semaglutide) unless indicated for diabetes mellitus treatment.

In addition to the medication recorded in trial [TCH-306](#), medications (including over-the-counter or prescription medicines) or vaccines (including COVID-19 vaccines) that the participant is receiving at the time of enrollment or receives during the trial must be recorded along with:

- Dates of administration including start and end dates
- Dosage information including dose and frequency

The following concomitant therapies are prohibited:

- hGH therapies other than lonapegsomatropin
- GH secretagogues
- Anabolic steroids other than when used as replacement therapies
- Biotin in doses higher than 0.03 mg/day from supplements. Higher doses of biotin may result in interference with commonly used biotinylated immunoassays, leading to false results.
- Cabergoline above 0.5 mg weekly or bromocriptine above 20 mg weekly due to their effects on lowering IGF-1 and GH hormonal concentrations and its independent effects on weight ([Abs 1998](#), [Korner 2003](#), [Thorner 1975](#))

The medical monitor should be contacted if there are questions regarding concomitant therapy.

## 7. DISCONTINUATION OF TRIAL INTERVENTION AND PARTICIPANT DISCONTINUATION/WITHDRAWAL

### 7.1. DISCONTINUATION OF TRIAL INTERVENTION

The investigator may discontinue treatment of a participant due to safety reasons e.g., AEs. If the participant agrees, the investigator may decide that the participant should continue the trial off treatment.

The investigator must stop the treatment for an individual participant in case of:

- Evidence of severe hypersensitivity to the trial drug
- Confirmed neutralizing anti-hGH antibodies
- Evidence of tumor growth or new onset malignancy
- Evidence of progression or new onset retinopathy
- Pregnancy

### 7.2. PARTICIPANT DISCONTINUATION/WITHDRAWAL FROM THE TRIAL

- A participant may withdraw from the trial at any time at the participant's own request or trial intervention may be withdrawn at the discretion of the investigator for safety, behavioral, or compliance reasons. This is expected to be uncommon.
- At the time of discontinuing from the trial, if possible, an early discontinuation visit should be conducted similar to the end-of-treatment visit, as shown in the SoA (Section 1.2).
- If the participant withdraws consent for disclosure of future information, the Sponsor may retain and continue to use any data collected before such a withdrawal of consent
- If a participant withdraws from the trial, the participant may request destruction of any samples taken and not tested, and the investigator must document this in the site trial records

### 7.3. LOST TO FOLLOW UP

A participant will be considered lost to follow-up if he/she repeatedly fails to return for scheduled visits and is unable to be contacted by the study site. The following actions must be taken if a participant fails to return to the clinic for a required study visit:

- The site must attempt to contact the participant and reschedule the missed visit as soon as possible, counsel the participant on the importance of maintaining the assigned visit schedule and ascertain whether the participant wishes to and/or should continue in the study.
- Before a participant is deemed lost to follow-up, the investigator or designee must make every effort to regain contact with the participant (where possible, 3 telephone calls, and if necessary, a certified letter to the participant's last known mailing address or local equivalent methods). These contact attempts should be documented in the participant's medical record.

Should the participant continue to be unreachable, he/she will be considered to have withdrawn from the study.

## 8. TRIAL ASSESSMENTS AND PROCEDURES

- Participants will continue to be identified with the same 8-digit participant number as in trial **TCH-306**. Likewise, the site numbers will remain the same.
- Trial assessments, procedures and their timing are summarized in the SoA. Protocol waivers or exemptions are not allowed.
- All lab sampling should be drawn in the morning (6:00-10:00 AM) as participants are required to attend in a fasting status having consumed only water for the last 8 hours
- Immediate safety concerns should be discussed with the Sponsor immediately upon occurrence or awareness to determine if the participant should continue or discontinue trial intervention.
- Adherence to the trial requirements, including those specified in the SoA Section [1.2](#), is essential and required for trial conduct.
- All screening evaluations must be completed and reviewed to confirm that potential participants meet the eligibility criteria. The investigator will maintain a screening log to record details of all participants screened and to confirm eligibility or record reasons for screening failure, as applicable.
- Procedures conducted, results obtained and recorded in the case report form (CRF) as part of the participation in trial TCH-306 obtained before signing of the informed consent form (ICF) will be utilized for screening or baseline purposes in this trial.

- CCI [REDACTED] CI [REDACTED]  
[REDACTED]
- The maximum amount of blood collected from each participant over the duration of the trial, will not exceed 300 mL.
- A diary will be handed out to the participants at each site visit. The participants will be instructed to enter every injection with the dose, date, and time together with the injection site i.e., right thigh, right abdomen, right buttock, left thigh, left abdomen, left buttock.

[figure not shown]
### 8.1. EFFICACY ASSESSMENTS

Planned timepoints for all assessments are provided in the SoA, Section [1.2](#).

#### 8.1.1. DXA Scan

To ensure consistency, a central reader will evaluate the DXA scans on an ongoing basis. It is recommended that DXA assessments are performed in a similar setting (time and hydration status) at each visit, using the same approved DXA machine throughout the trial. Sites should be following the DXA manufacturer's guideline for maintenance, calibration, and quality control, as well as the trial-specific guidelines as provided by the central reader in trial manuals.

Cross-calibration phantoms will be distributed to all sites using a scanner that was not cross-calibrated during TCH-306 to ensure consistency. DXA scans cannot be performed on participants who are pregnant or suspected to be pregnant.

### 8.1.3. Clinical Efficacy Laboratory Tests

- Detailed blood sampling, processing, and assaying of samples will be provided in the Laboratory Manual.
- See Appendix 2/Section 10.2 for the list of clinical laboratory tests to be analyzed at the central laboratory.

## 8.2. SAFETY ASSESSMENTS

Planned timepoints for all safety assessments are provided in the SoA (Section 1.2).

### 8.2.1. Physical Examinations

- Weight [with light clothes] will be measured and recorded as outlined in the SoA (see Section 1.2).
- A physical examination will include assessments of the skin (including injection site reaction assessment), head, ears, eyes, nose, throat, neck / thyroid, lymphatic, cardiovascular, respiratory, abdomen, genitourinary, nervous system, musculoskeletal, extremities as outlined in the SoA see Section 1.2. Clinically significant abnormalities must be reported as an AE in accordance with this protocol.

### 8.2.2. Vital Signs

- Vital signs will be obtained as outlined in the SoA, see Section 1.2. Systolic and diastolic blood pressure (BP) and pulse rate should be preceded by at least 5 minutes of rest and assessed with an automated device. Manual techniques will be used only if an automated device is not available.

### 8.2.3. Electrocardiograms

- 12-lead ECG will be obtained as outlined in the SoA (Section 1.2). Clinically significant abnormalities must be reported as an AE in accordance with this protocol.

### 8.2.4. Clinical Safety Laboratory Tests

- See the SoA (Section 1.2) for the timing and frequency of blood sampling.
- All lab sampling should be performed in the morning as participants are required to attend in a fasting status.
- Detailed blood sampling, processing, and assaying of samples will be provided in the Laboratory Manual.
- The investigator must review the laboratory report, document this review, and record any clinically significant changes occurring during the trial as an AE. The laboratory reports must be filed with the source documents.
- Repeat or unscheduled samples may be taken for safety reasons or for technical issues with the samples.
- Participants who are not on glucocorticoid replacement therapy and are diagnosed with low morning cortisol may undergo an ACTH stimulation test at any time during the trial
- See Appendix 2/Section 10.2 for the list of clinical laboratory tests to be analyzed at the central laboratory.

### **8.2.5. Pregnancy Testing**

- Pregnancy test (hCG) should be performed for females of childbearing potential as outlined in the SoA (Section 1.2).
- Additional testing is required if menstrual period is missed, or pregnancy is suspected.
- Pregnancy test will not be required for women who are surgically sterile, with permanent hypogonadism with proven cause (for example have undergone a hysterectomy or bilateral tubal ligation) or above the age of 50 who have been without a menstrual period for at least 12 months.

## **8.3. ADVERSE EVENTS SERIOUS ADVERSE EVENTS, AND OTHER SAFETY REPORTING**

The definitions of AEs and SAEs can be found in Appendix 3/Section 10.3.

AEs will be reported by the participant (or, when appropriate, by a caregiver).

The investigator is responsible for detecting, documenting, and recording events that meet the definition of an AE or SAE and remains responsible for following up on all AEs including AEs that are serious, considered related to the trial treatment or trial procedures, or that caused the participant to discontinue the trial treatment (see Section 7 and Section 8.3.3).

The method of recording, evaluating, and assessing causality of AEs and SAEs and the procedures for completing and transmitting SAE reports are provided in Appendix 3/Section 10.3.

### **8.3.1. Time Period and Frequency for Collecting AE and SAE Information**

All AEs will be collected until the first follow-up visit (i.e., 2 weeks after the last administration of trial drug or trial discontinuation/ termination, whichever is earlier). After this period, investigators should only report SAEs that are attributed to prior study treatment.

All SAEs will be reported to the Sponsor or designee immediately and within 24 hours of awareness, as indicated in Appendix 3/Section 10.3. The investigator will submit any updated SAE data to the Sponsor within 24 hours of it being available.

Investigators are not obligated to actively seek information on AEs after the first follow-up visit. However, if the investigator learns of any SAE, including a death, at any time after a participant has been discharged from the trial, and he/she considers the event to be reasonably related to the trial intervention or trial participation, the investigator must notify the Sponsor within 24 hours of awareness.

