## 4. TRIAL DESIGN

### 4.1. OVERALL DESIGN

This is a phase 3 open-label multicenter extension trial designed to evaluate the long-term safety and efficacy of lonapegsomatropin administered once-weekly. The trial participants are adults (males and females) with GHD having completed the treatment period in trial **TCH-306** (foresiGHt). Therefore, participants are either previously treated with lonapegsomatropin, a daily somatropin product, or placebo in trial TCH-306.

The trial duration will up to 60 weeks in total and consist of:

- Screening Period – up to 3 weeks starting at Screening Visit. A Screening Visit is not needed if all inclusion and no exclusion criteria were met at V7 and if V8 occurs  $\leq$ 8 weeks after V7.
- Treatment Period – (52 weeks), consisting of:
  - Dose Titration Period – 12 weeks, three visits
  - Dose Maintenance Period – 40 weeks, four visits
- Follow-up Treatment-free Period – (30-37 days/4-5 weeks), consisting of:
  - Two weeks after the last dose of trial drug: Collection of AEs remotely
  - 30-37 days after the last dose of trial drug: Samples for ADA and pregnancy test (for females of childbearing potential)

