#### **10.3.2.1. Adverse Event Reporting Period**

The AE reporting period continues without interruption after completion of trial TCH-306 and ends 2 weeks following the last injection of trial drug in trial TCH-306EXT or trial discontinuation/ termination, whichever is earlier. After this period, investigators should only report SAEs that are attributed to trial treatment.

If the electronic data capture (EDC) system is not available, the investigator should report these events directly to the Sponsor outlined in Section [10.3.4.2](#).

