#### 10.3.3.2. Recording Procedures for All Adverse Events

AEs will be documented in response to questions about the participant’s well-being and whether any changes in well-being have occurred since the previous visit. Additionally, at each visit, site staff will review participant diary data with the participant, to determine if diary entries reflect any AEs. AEs, including SAEs, will be documented from start of trial participation until 2 weeks after the last dose of trial drug was taken. All AEs must be recorded on the appropriate eCRF. AEs either observed by the investigator or reported by the participant must be recorded regardless of causality. The following attributes must be documented for each AE:

Trial ID

Subject number

AE Term

For SAEs: Description

Onset date

Resolution date, if applicable

Severity

Causality (relationship to the trial drug)

Outcome

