11.11. SAFETY ANALYSIS

Unless otherwise specified, safety analyses will be performed using the Safety Analysis population for the extension period. The safety parameters will include adverse events (AEs), clinical laboratory, vital sign, electrocardiographic (ECG) parameters, MRI, fundoscopy, immunogenicity, and other safety parameters if collected. For safety endpoints, all analyses will be based on the observed data (i.e., with no imputation of missing data), unless otherwise stated. These summaries will be presented by treatment group in the extension period.

Adverse events will be coded by system organ class (SOC) and preferred term (PT) using the Medical Dictionary for Regulatory Activities (MedDRA) Version 26.0.

An extension period AE (classified by preferred term) will be considered as treatment emergent adverse event (TEAE) if it occurred on or after the first dose of open-label lonapegsomatropin and was not present prior to the first dose of open-label lonapegsomatropin, or it was present at the first dose of open-label lonapegsomatropin but increased in severity during the study through 14 days after the last dose of treatment on the extension period.

A TEAE that started on or after the first dose date of open-label lonapegsomatropin will be counted as extension period TEAE.

- Summary of TEAEs by treatment
- TEAEs by treatment, SOC and PT (sorted by descending frequency by SOC and PT)
- TEAEs by treatment, SOC and PT Reported by > 5% of subjects in any treatment group
- Related TEAE by treatment, SOC and PT
- Serious TEAEs by treatment, SOC and PT (sorted by descending frequency by SOC and PT)
- Serious Related TEAEs by treatment, SOC and PT (sorted by descending frequency by SOC and PT)
- AEs leading to death by treatment, SOC and PT (sorted by descending frequency by SOC and PT)
- TEAEs leading to discontinuation of study by treatment, SOC and PT (sorted by descending frequency by SOC and PT)
- TEAEs leading to discontinuation of treatment by treatment, SOC and PT (sorted by descending frequency by SOC and PT)
- TEAEs by treatment and PT (sorted by descending frequency of PT)
- Related TEAEs by treatment and PT (sorted by descending frequency of PT)
- Serious TEAEs by treatment and PT (sorted by descending frequency of PT)
- Deaths by treatment

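### Protocol 8.3.1 and 10.3.2.1 can be read as ending AE collection when a participant leaves the trial, in conflict with the two-week post-dose window given elsewhere

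*Protocol*

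**What the plan says.** Two protocol sections carry the clause at issue, "or trial discontinuation/ termination, whichever is earlier".

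- Protocol 8.3.1: "All AEs will be collected until the first follow-up visit", which it then explains as "2 weeks after the last administration of trial drug or trial discontinuation/ termination, whichever is earlier".
- Protocol 10.3.2.1: the reporting period "ends 2 weeks following the last injection of trial drug in trial TCH-306EXT or trial discontinuation/ termination, whichever is earlier".

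Both add that, once this period is over, only serious AEs (SAEs) attributed to treatment need reporting.

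Other places describe the window without any cut-off at discontinuation.

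- Protocol 10.3.3.2: "AEs, including SAEs, will be documented from start of trial participation until 2 weeks after the last dose of trial drug was taken".
- Protocol 4.1, under the follow-up period: "Two weeks after the last dose of trial drug: Collection of AEs remotely".
- Protocol 1.2 (Schedule of Activities): V16, the first follow-up contact, is remote, falls 14 to 16 days after the last dose and includes AE review.

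Protocol 7.2 gives early leavers, where possible, a visit modelled on the end-of-treatment visit, which the Schedule of Activities times at 4 to 5 days after a dose. It neither mentions nor excludes a later AE contact.

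**The concern.** If the clause in 8.3.1 and 10.3.2.1 means what it most naturally says, a participant who leaves a few days after an injection has no further AE collection beyond treatment-attributed SAEs. A participant who completes is followed for the full two weeks. Sites that work from 10.3.3.2 and sites that work from 8.3.1 would stop at different times for the same kind of participant.

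Safety is the primary objective and AEs are the first endpoint listed. What would be lost is specific: non-serious AEs, and SAEs (including deaths) not attributed to treatment, that begin between leaving and day 14. Protocol 10.3.4.2 otherwise asks for SAEs to be reported whatever the suspected cause.

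Leaving the trial is also not the same as refusing a call. The clause covers termination, and Protocol 10.1.9 lets the sponsor close a site or end the trial at any time. Participants whose follow-up ends that way have declined nothing.

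**Working it through.** The plan states no figure on this point, so there is nothing to reproduce. The check compares the passages and then sizes the possible loss.

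**Step 1. The end points side by side**

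| Place | End of AE collection | Cut-off at discontinuation? |
|---|---|---|
| Protocol 8.3.1 | First follow-up visit, explained as two weeks after last dose or discontinuation/termination, the earlier | Yes, on the natural reading |
| Protocol 10.3.2.1 | Two weeks after last injection or discontinuation/termination, the earlier | Yes, on the natural reading |
| Protocol 10.3.3.2 | Two weeks after last dose | No |
| Protocol 4.1 | Remote AE contact two weeks after last dose | No |
| Protocol 1.2 (V16) | Remote AE contact, days 14 to 16 after last dose | No |

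On the natural reading, 8.3.1 also disagrees with itself. It ties the end of collection to the first follow-up visit, which the Schedule of Activities fixes by the last dose and not by the date of leaving.

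**Step 2. Days lost per early leaver**

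Days lost = max(0, 14 − days from last dose to leaving the trial).

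| Leaves on day | Days lost of 14 | Share |
|---|---|---|
| 0 | 14 | 100% |
| 4 | 10 | 71% |
| 5 | 9 | 64% |
| 7 | 7 | 50% |
| 14 or later | 0 | 0% |

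If the early discontinuation visit keeps the end-of-treatment timing (4 to 5 days after a dose) and counts as the date of leaving, 9 to 10 days are lost.

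**Step 3. Total loss**

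- Participants: 220 from TCH-306 plus 13 commercial switch = 233 (SAP section 4).
- Early leavers: 5% to 15%. This is an assumption, because the documents give no rate.
- Days lost each: 9 to 14, which corresponds to leaving on day 5 back to day 0.
- Low end: 233 × 0.05 × 9 = 104.9, about 105 person-days.
- High end: 233 × 0.15 × 14 = 489.3, about 489 person-days.

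**Step 4. Against planned observation**

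- Per participant: first to last of 52 weekly doses is 51 × 7 + 1 = 358 days; adding 14 gives 372.
- All participants: 233 × 372 = 86,676 person-days.
- Share of all planned AE observation: 105 / 86,676 = 0.12%; 489 / 86,676 = 0.56%.
- Share of the planned post-dose window alone (233 × 14 = 3,262 person-days): 105 / 3,262 = 3.2%; 489 / 3,262 = 15%.

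**The case against.** **The clause can be read another way.** The words about two weeks may govern both items, giving two weeks after the earlier of last dose and discontinuation. Because the last dose cannot come after discontinuation, that is simply last dose plus 14 days. It agrees with 10.3.3.2, 4.1 and V16, and most of the shortfall disappears. This stands as a possible reading, so a loss of data is not proven. It does, however, leave the choice of the earlier date with no work to do, which is why the other reading is the more natural one. The text does not settle the matter.

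**The follow-up call may already cover early leavers.** V16 is timed from the last dose and nothing limits it to completers. That is so, but 8.3.1 and 10.3.2.1 as worded give a site grounds not to collect AEs at it.

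**The loss is narrow.** This stands in full. Participants who stop the drug but stay in the trial (Protocol 7.1) keep the whole window. Treatment-attributed SAEs are still reported. An AE that prompts someone to leave begins before the cut-off and is captured on either reading. Protocol 7.2 expects withdrawal to be uncommon.

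**Two stronger inferences are not supported.**

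- A reader might take the SAP as a further direct contradiction. SAP 11.11 does refer to events that "increased in severity during the study through 14 days after the last dose of treatment on the extension period", but that phrase attaches to pre-existing events that worsen, and it belongs to an analysis definition, not a collection rule. An analysis window wider than some participants' follow-up is not in itself an inconsistency.
- A reader might infer that the lost time is concentrated in those at highest risk because people often leave on account of AEs. The documents give no reasons for leaving by frequency, so this is plausible but undocumented.

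**Conclusion.** The two clauses are ambiguous. On their most natural reading they conflict with Protocol 10.3.3.2, with the remote AE contact in 4.1 and the Schedule of Activities, and with the anchor to the first follow-up visit in 8.3.1 itself. The passages need to be reconciled.

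The size is modest: roughly 0.1% to 0.6% of planned AE observation time. This rests on the assumed 5% to 15% of 233 leaving the trial, on the natural reading of the clause, and on departure within 5 days of the last dose. Later departure lowers the loss, and some of the time could not be recovered in any case, because some leavers will be lost to follow-up or will refuse contact. The full 14 days per leaver is a maximum, reached only by leaving on a dosing day.

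The documents do not support a conclusion that the primary safety results would be materially distorted. The point is worth acting on because the shortfall falls only on early leavers, it concerns the primary objective, and it is cheap to remove.

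**What to change.** In Protocol 8.3.1 and 10.3.2.1, delete "or trial discontinuation/ termination, whichever is earlier". In both, state that all AEs, serious or not and whatever the attribution, are collected through 14 days after the last dose for every participant. Say explicitly that this includes early leavers and those whose participation ends through site or trial termination.

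Name the existing remote V16 contact as the means, and add to Protocol 7.2 that it applies after an early discontinuation visit. Allow collection to end sooner only on death, loss to follow-up or withdrawal of consent to contact. Protocol 4.1 and 10.3.3.2 can stay as they are.

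The cost is a wording change in two sections, a cross-reference in a third, and about one call per early leaver. AE counts may rise slightly.
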